- 11. Explore the Clinical Trials Transformation Initiative (CTTI) and the FDA supported Sentinel Data Partners' ability to successfully conduct a pragmatic trial to answer important questions to improve public health

Prospective, randomized, open-label education intervention trial. Patients with AF and a CHA₂DS₂-VASc score of 2 or greater will be randomized in a 1:1 ratio to (a) the early intervention arm: early

patient and provider educational interventions for those patients identified at the time of randomization and (b) the delayed intervention arm: usual care followed by provider education intervention 12 months after at least 80% of early intervention mailing has occurred (eligibility status of these patients will be assessed at time of delayed mailing). All inclusion criteria, exclusion criteria, and outcomes will be determined through claims data. The primary outcome is the proportion of AF patients with evidence of at least one OAC prescription fill over the course of the follow-up through the date on which at least 80% of eligible study participants have at least 12 months of follow-up time. A total of approximately 80,000 patients will be enrolled within multiple major health plans across the United States. Follow-up for the

primary outcome and secondary outcomes will be assessed 12 months after the date on which at least 80% of eligible early intervention participants were mailed the early intervention materials. The randomization will be performed by the central coordinating center (Harvard Pilgrim), and statistical analyses will be performed by the Duke Clinical Research Institute. A second exploratory assessment of the primary and secondary endpoints will be performed once at least 80% of participants have at least 24 months of follow-up time to assess the durability and longer-term outcomes of the effect of the education intervention. Because the

Sentinel Distributed Database will be used for follow-up information, and this information is refreshed approximately

Study Design:

quarterly and this is done on separate timetables for the different health plans, it is likely that when at least the required follow-up

IMPACT-AFib

	time is available for at least 80% of people, there will be more than		
	12 or 24 months of follow-up for over 80% of people. All possible		
	person-time will be used to assess participants' outcomes (patients		
	will have different duration of follow-up).		

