The providers of patients in the delayed cohort who did not receive OAC medication during the course of the 12-month study period and meet our inclusion criteria will receive the delayed intervention: the provider-only education intervention, a one-time mailing administered 12 months after at least 80% of early intervention mailing have occurred (patients will not receive any educational materials unless no provider can be identified for a mailing). We intend to assess the primary and secondary endpoints again once at least 80% of patients have at least 24 months of follow-up time to assess the durability and longer-term outcomes of the effect of the patient- and provider-level education intervention, as well as the use of OAC following the delayed provider-level education intervention. However, as this second assessment is exploratory, we may not conduct these analyses if the results of the primary outcome are null.

Because the Sentinel Distributed Database will be used for follow-up information, and this information is refreshed approximately quarterly and this is done on separate timetables for the different health plans, it is likely that when at least the required follow-up time is available for at least 80% of people, there will be more than 12 or 24 months of follow-up for over 80% of people. All participants' outcomes will be assessed using all possible person-time; patients will have different duration of follow-up and that will be accounted for in the analyses.

A schematic diagram below shows the design of the early intervention period of the study over the course of the follow-up through the date on which at least 80% of eligible study participants have at least 12 months of follow-up time:

^{*}Baseline characteristics of delayed and early intervention cohorts will be taken from the same time point at randomization from a dataset that is archived at randomization, while exclusion criteria for evidence of OAC medication fill or P2Y12 antagonist use was determined at randomization for the early intervention cohort and approximately 12 months post-randomization for the delayed intervention cohort.

[figure not shown]
For analysis, treatment status is at time of randomization or corresponding early intervention mailing; for the delayed intervention mailing it is prior to mailing.

^{**}All possible person-time will be used to assess participants' outcomes (patients will have different duration of follow-up).

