A schematic diagram below shows the design of the delayed intervention portion of the study:

*All possible person-time will be used to assess participants' outcomes (patients will have different duration of follow-up).

For analysis, treatment status is at time of randomization or corresponding early intervention mailing; for the delayed intervention mailing it is prior to mailing.

VII. STUDY POPULATION

All inclusion and exclusion criteria will be determined by claims data. For entry into the study, the following criteria will be met:

A. INCLUSION CRITERIA

- 1. Two or more diagnoses of AF (ICD-9 and/or ICD-10 codes) at least one day apart and with at least one diagnosis within the last 12 months prior to the last date in the current approved data used for cohort identification
- 2. CHA₂DS₂-VASc score of 2 or greater
- 3. Medical and pharmacy insurance coverage of at least the prior year as identified via administrative claims databases of one of the participating Data Partners as of the date of randomization
- 4. Age 30 years or greater as of the last date in the current approved data used for cohort identification

B. EXCLUSION CRITERIA

- 1. Evidence of OAC medication fill (defined as 1 OAC dispensing or 4 INR tests) during the 12 months prior to randomization (determined at randomization for the early intervention cohort and 12 months post-randomization for the delayed intervention cohort)
- 2. Conditions other than AF that require anticoagulation, including treatment of deep venous thrombosis, pulmonary embolism, or ever having had a mechanical prosthetic heart valve prior to the last date in the current approved data used for cohort identification
- 3. Pregnancy within 6 months of the last date in the current approved data used for cohort identification
- 4. Any known history of intracranial hemorrhage prior to the last date in the current approved data used for cohort identification
- 5. Hospitalization for any bleeding within the last 6 months of the last date in the current approved data used for cohort identification
- 6. Patients with recent P2Y12 antagonist use (i.e. clopidogrel, prasugrel, ticlopidine, or ticagrelor within 90 days of the last date in the current approved data used for cohort identification

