The waiver of informed consent is consistent with the approach that has been taken in several similar clinical trials, the first using individual patient randomization, the others cluster randomized:

- 1. UH3 Pragmatic Trial of Population-based Programs to Prevent Suicide Attempt (NCT02326883)
- 2. The HMO Research Network CERT: A randomized trial of direct-to-patient communication to enhance adherence to beta-blocker therapy following myocardial infarction (NCT00211172)
- 3. MI FREE: A Randomized Evaluation of First-dollar Coverage for Post-MI Secondary Prevention Therapies (NCT00566774)
- 4. STOPCRC: Strategies and Opportunities to Stop Colon Cancer in Priority Populations (NCT01742065)

XIII. INDEPENDENT ADVISORY COMMITTEE

An independent advisory committee (IAC), consisting of members independent from the study team and with expertise in statistics, anticoagulation for atrial fibrillation, engagement, health plan management, and/or in practical clinical trials, will serve to enhance patient safety and trial integrity. The IAC will meet with study leadership at least twice. The first meeting will occur before intervention materials are mailed, and the second will take place two months after all mailings are sent. In addition, other meetings will occur if deemed necessary by the IAC chair, study leads and/or the FDA. The study team will provide the IAC with the study protocol before any intervention materials are mailed and will brief the IAC on any issues (or lack thereof) that have been raised 2 months after the last mailing has occurred. The IAC will advise on concerns that arise. An IAC charter describes the roles, responsibilities, and operations of the IAC.

XIV. STATISTICAL CONSIDERATIONS

A. SAMPLE SIZE AND POWER CALCULATIONS

Our target sample size is 80,000 patients. All enrolled patients and/or their providers will be targeted by mailing (early or delayed) provided they are eligible at time of mailing and able to be contacted.

1. Primary Endpoint

The following assumptions were used to determine the sample size and power for the primary endpoint assessing the proportion of AF patients with evidence of at least one OAC prescription fill through the date on which at least 80% of eligible study participants have at least 12 months of follow-up time:

- 33% OAC initiation rate in the delayed intervention arm over the first year of the study

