6. Patients with recent P2Y12 antagonist use (i.e., clopidogrel, prasugrel, or ticagrelor within 90 days of prior to randomization)

F. STUDY DESIGN AND DURATION

As described in detail in the protocol, the study is a prospective, randomized, and open-label educational intervention trial. Patients with AF and a CHA₂DS₂-VASc score of 2 or greater were randomized in a 1:1 ratio to an early intervention cohort and a delayed intervention cohort within each participating health plan. The definition for OAC medication fill was an OAC medication dispensing or at least 4 INR tests in the claims data.³ The claims records of the patients randomized to the early intervention cohort were then linked to “fresh” (i.e., about 1 month old) pharmacy claims data at the time of randomization. Patients without evidence of an OAC medication fill during the 12 months prior to randomization were included in the patient-level and provider-level early educational intervention (patients randomized to this early intervention with evidence of an OAC medication fill during the 12 months prior to randomization were excluded from the trial). In addition to usual care, these patients and their providers received a one-time mailing at trial start. There were two waves of mailing for the early intervention cohort at most sites due to the practical challenges of claims data: the patients were assigned to wave 1 if they had a provider easily identified in the data (i.e., the provider associated with the most recent AF diagnosis is indeed an individual provider), and they were assigned to wave 2 if it was difficult to identify a provider (e.g., the first identified provider is actually a facility). Follow-up time started on the date of the respective wave 1 and wave 2 mailings for the early intervention patients.

The delayed intervention cohort will have received usual care over the initial study period. After the date on which at least 80% of all eligible study participants have at least 12 months of follow-up time, the treatment status of the delayed intervention group will be assessed via the Sentinel data available at that time, in addition to “fresh” pharmacy claims data. The providers of patients in the delayed cohort who did not receive OAC medication during the course of follow-up and still meet all inclusion criteria will receive the provider-only education intervention (patients will not receive the educational materials unless no provider can be identified for a mailing).

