[figure not shown]
Details on the analyses are provided in Section II. Here we describe the data sources for the **modified intention-to-treat** (primary) and **as-randomized** (sensitivity) analyses. Similar to early intervention cohort, the patients in the delayed intervention cohort will be assigned to wave 1 or wave 2 (“pseudo”

³Not all OAC dispensings are captured in pharmacy claims, particularly, for warfarin due to some patients paying for medication out of pocket. INR tests are assumed indicative of OAC fills that were not billed through the claims. Four INR tests or values within a 12-month period will be used as a proxy since that is roughly the number of tests administered in the process of stabilizing dose.

wave assignments) depending on the difficulty in identifying the patient's provider (the intent is to handle them the same way as was done for the early intervention arm, for the modified intention-to-treat analysis). The follow-up for the delayed intervention patients will start on the date the wave 1 or 2 mailings took place for a given Data Partner's early intervention cohort. For both early and delayed intervention cohorts, any patients who die, are disenrolled, or get started on OAC between the randomization and early intervention mailing will be excluded from the analysis at each Data Partner. For both the early and delayed arms, exclusion criteria that are based on member medical history were assessed at the time of randomization. For the early intervention cohort, enrollment and treatment status were assessed at randomization for all and re-assessed at the wave 2 time point at some of the sites (this was at site discretion, in response to the lag between wave 1 and 2 mailings). The enrollment and treatment status of the delayed intervention cohort will be examined for eligibility at the same time point as the early intervention patients, meaning at the time of mailing per Data Partner, via the locked data (using the wave 1 and 2 dates).

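### The delayed-mailing rule names only the inclusion criteria, while the protocol elsewhere requires eligibility at mailing; new hemorrhage or recent bleeding may therefore go unscreened

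*SAP*

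**What the plan says.** **Mailing rule.** SAP I.F gives the delayed mailing to providers of delayed-arm patients "who did not receive OAC medication during the course of follow-up and still meet all inclusion criteria will receive the provider-only education intervention". Protocol VI likewise says that providers of patients who received no OAC over the study period "and meet our inclusion criteria will receive the delayed intervention". If no provider can be identified, both documents let the materials go to the patient.

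**Eligibility at mailing.** The Protocol Synopsis (Study Design) says that the "eligibility status of these patients will be assessed at time of delayed mailing". Protocol XIV.A says: "All enrolled patients and/or their providers will be targeted by mailing (early or delayed) provided they are eligible at time of mailing".

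**Look-back dates.** Protocol VII lists inclusion and exclusion criteria separately. Exclusion 5 reads "Hospitalization for any bleeding within the last 6 months of the last date in the current approved data used for cohort identification". The exclusions for other anticoagulation indications, pregnancy and intracranial hemorrhage end at the same data cut. SAP I.F adds, for both arms, that "exclusion criteria that are based on member medical history were assessed at the time of randomization".

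**What is determined later in the delayed arm.** A footnote to the schematic in Protocol VI and SAP I.F names two exclusions determined about a year after randomization in the delayed cohort: OAC fill and P2Y12 antagonist use. Hemorrhage and bleeding are not named.

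**The concern.** The two descriptions of who is mailed can produce different lists. Someone programming from SAP I.F would check OAC status and the inclusion criteria. Someone programming from the Synopsis or XIV.A would check eligibility, which on a plain reading includes the exclusions. Neither is told the date at which the hemorrhage and bleeding look-backs should end for a mailing sent a year or more after the cohort was drawn.

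At stake is the consistency of the mailing with the trial's own safeguards. Per Protocol VIII.B, the delayed letter names the provider's patients who are untreated and at risk of stroke. The early mailing went out only after the hemorrhage and bleeding exclusions had been applied. The delayed mailing may reach patients whom those exclusions would have removed. Consent is waived (Protocol XII), partly because the intervention is judged very low in risk, so the screen that supports that judgment should be unambiguous at both mailings.

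**Working it through.** No figure in the plan is in dispute, so the check sets the passages side by side.

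1. **Would re-checking the inclusion criteria remove a patient with a new hemorrhage?** No. The four inclusion criteria concern AF diagnoses, CHA₂DS₂-VASc of at least 2, coverage and age. In SAP Table 1 the stroke component includes hemorrhage codes (I60, I61 and I62.9). A new intracranial hemorrhage can therefore raise the score but not lower it.

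2. **Worked case.** Take a delayed-arm patient with an intracranial hemorrhage in month 8 of follow-up and no OAC, who is still insured and still coded for AF.
   - SAP I.F and Protocol VI as written: no OAC, inclusion criteria met, so **listed**.
   - Synopsis and XIV.A, with look-backs ending at the data used for the delayed mailing: the hemorrhage exclusion applies, so **removed**.
   - Synopsis and XIV.A, with look-backs ending where Protocol VII puts them: the event falls after the original cut and is not seen, so **listed**.

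   Three readings give two different results. Eligibility at mailing settles the matter only if the date is also stated.

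3. **Bleeding hospitalizations.** The window is 6 months. Suppose the mailing is at month 12 and the look-back ends there. A bleed in month 9 is 12 − 9 = 3 months old and would exclude. A bleed in month 3 is 12 − 3 = 9 months old and would not. The gap concerns bleeds in the last 6 months before the mailing, not every bleed during follow-up.

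4. **P2Y12 use.** Three places give three timings. Protocol VII.B ties the 90 days to the cohort-identification data cut. SAP I.E ties them to randomization. The footnote has the criterion determined about a year later in the delayed arm. The footnote says when the check is made, not where the 90 days end.

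5. **Reasons for not mailing.** The list in Protocol IX covers death, disenrollment, change of plan, recent anticoagulant dispensing, address problems and do-not-contact status. It contains no bleeding event, though it is stated to be possibly incomplete.

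6. **Are the data available?** Largely. Hospitalizations for bleeding and hemorrhagic stroke are ascertained from claims as outcomes (Protocol XVI.C, SAP II.D.4). SAP I.D says the fresh linked data cover pharmacy and enrollment only, and that routine Sentinel data are several months old. The most recent bleeds could still be missed, which is another reason to state the date.

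7. **Size.** On the plan's own figures, the delayed list before any exclusion would be about 40,000 × (1 − 0.30) × (1 − 0.33) = 18,760. This takes half of the 80,000 target, 30% attrition and 33% OAC initiation, applied in turn. Each 1% of that list is about 188 patients. The documents give no rate of new hemorrhage or recent bleeding in untreated patients, so this is a scale and not a count.

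**The case against.** The strongest reply is that the protocol already requires what is asked. The Synopsis and XIV.A make mailing conditional on eligibility, and the SAP is to be read with the protocol. The vocabulary is also loose: Protocol IX calls the no-OAC rule an inclusion criterion although it is formally exclusion 1, so the wording in SAP I.F may be shorthand for full eligibility. Inclusion criteria 1 and 4 share the same data-cut anchor as most exclusions. If that anchor is frozen, re-checking inclusion means little; if it moves forward, it arguably moves for the exclusions too. The SAP sentence on medical-history exclusions sits in a paragraph on analysis data sources, so it does not govern the mailing. The schematic of the delayed portion could not be read for this review and may show a screening step. Finally, the letter normally goes to a clinician, with a mailer for explaining why the patient is untreated.

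Most of this stands, and it rules out some stronger readings. A reader might infer that nothing but OAC status and inclusion is looked at again; the P2Y12 footnote and the eligibility sentences contradict that. A reader might infer that patients with hemorrhage will be mailed; the text shows only that they may be. A reader might also infer that the 24-month assessment is compromised because the two mailings reach differently selected patients. That difference is there by design: the delayed mailing goes only to patients still untreated after about a year, and normally to providers alone. Re-applying exclusions would not remove it, and the assessment is exploratory and may not be run.

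The reply does not remove the conflict. If SAP I.F is shorthand, it does not say so, and no passage gives the date on which the hemorrhage and bleeding exclusions would be re-evaluated.

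**Conclusion.** The point holds as a conflict between passages with a possible safety consequence. SAP I.F and Protocol VI select on OAC status and the inclusion criteria; the Synopsis and Protocol XIV.A require eligibility at mailing; the hemorrhage, bleeding and other medical-history exclusions keep their original data cut. Under SAP I.F as written, patients with a new intracranial hemorrhage or a bleeding hospitalization in the preceding 6 months may be listed.

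The number affected cannot be derived from the documents. The 12-month primary comparison is untouched, because eligibility for that analysis is fixed at randomization or at the date of the corresponding early mailing. The conclusion assumes that the unreadable schematic and the external code list do not already specify a re-screen. It should be resolved before the delayed mailing list is drawn.

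**What to change.** Reconcile Protocol VI, SAP I.F and the schematic footnotes with the Synopsis and Protocol XIV.A.

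- In Protocol VI and SAP I.F, refer to full eligibility under Protocol VII, inclusion and exclusion criteria together, in place of the inclusion criteria alone. This matches what the Synopsis and XIV.A already say. If the sponsor intends a particular exclusion not to apply at the delayed mailing, say so and amend those two places.
- For each criterion, state the data date that ends its look-back for the delayed mailing. Resolve the three P2Y12 timings at the same time.
- Report the number removed from the delayed mailing list, by reason.
- Add that this rule decides who is mailed and not who enters the 12-month analysis.

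The cost is a few sentences, a re-run of the existing cohort-identification code on refreshed data, and a slightly shorter mailing list.

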The delayed intervention cohort will receive usual care over the initial study period. After the date on which at least 80% of eligible study participants have at least 12 months of follow-up time, "fresh" pharmacy claims data for the delayed intervention cohort that was generated and locked at the time of randomization will be used to assess trial eligibility, and those patients without evidence of an OAC medication fill during the 12 months prior to randomization will be included in the primary and secondary analyses as the delayed intervention arm. Patients randomized to the delayed intervention arm with evidence of an OAC medication fill during the 12 months prior to randomization will be excluded from the trial and will not be included in analyses. The baseline characteristics of the delayed intervention patients will be examined at the same time point as the early intervention patients, meaning at the time of randomization. The primary outcome is a comparison of the proportion of patients not on OAC during the 12 months prior to randomization, who were started on OAC over the course of the follow-up through the date on which at least 80% of eligible study participants have at least 12 months of follow-up time in the early versus the delayed intervention arm. A total of approximately 80,000 patients (randomized 1:1) across all participating Data Partners (Aetna, Harvard Pilgrim, HealthCore, Humana, and Optum) will be enrolled from participating Data Partners across the United States. Similar to the early intervention cohort, the patients in the delayed intervention cohort will be assigned to wave 1 or wave 2 ("pseudo" wave assignments) depending on the difficulty in identifying the patient's provider (the intent is to handle them the same way as was done for the early intervention arm). The follow-up for the delayed intervention patients will start on the date the wave 1 or 2 mailings take place for a given Data Partner's early intervention cohort. The follow-up time for the primary outcome will be 12 months from the date at which at least 80% of eligible study participates are enrolled (date on which early intervention materials are mailed).

[figure not shown]

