All primary analyses will be based on modified intention-to-treat (mITT) principle (i.e., all identified early intervention patients who met eligibility and were mailed the intervention will be included; using “pseudo” wave assignments, all identified delayed intervention patients who met eligibility at the time of corresponding early mailings will be included). Since the additional exclusions after randomization will be applied in the same way, using the same time points for both the early and delayed intervention groups, we expect there will be no effect from these additional exclusions on the randomization. The mITT analysis will include the following:

- Early intervention members who were mailed a letter, with follow-up beginning on the date of mailing (up to two dates per site and the dates varied by site).
- Delayed intervention members who were not on treatment at the date of mailing (wave assignments were made for the delayed as described earlier in section I.F) with follow-up beginning on that date.

An as-randomized analysis will be performed for an incident occurrence of the primary endpoint as a sensitivity analysis (using a washout of 365 days). Randomization occurred prior to treatment status assessment per the study design. Therefore, the as-randomized analysis will include people who were on treatment as well as others who were not truly eligible for the study (e.g., had incomplete or invalid addresses or had a “do not contact” status).

Potential sensitivity analysis for mITT analysis: There may be differential loss to follow up between the early and delayed intervention groups because some members did not have valid mailing addresses, though we did not assess the addresses of the members in the delayed intervention arm at the time of early intervention mailings. It is not possible to retrospectively ascertain the address status of the delayed intervention group as of the date on which mailing would have occurred for that group. We can estimate the magnitude by referring to the early intervention group, and in the early intervention group, we can compare the baseline characteristics and experience of the individuals who had no valid address to those who do.

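### The documents give conflicting timings and data sources for the OAC-free and enrolment screen that defines the primary mITT set, and name no source that applies the common exclusion to all early-arm patients

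*SAP*

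**What the plan says.** Some text prescribes a symmetric screen:

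- SAP I.F says of both cohorts that patients who die, disenroll or "get started on OAC between the randomization and early intervention mailing will be excluded from the analysis at each Data Partner".
- SAP II says that the post-randomization exclusions are applied in the same way, "using the same time points for both the early and delayed intervention groups", and expects no effect on the randomization for that reason.
- A note to the schematics in Protocol VI and SAP I.F sets treatment status for analysis at randomization or the corresponding early mailing.

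Other text describes operations that differ by arm or cannot deliver that rule:

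- Early arm, SAP I.F: status was checked for every patient when randomized, then "re-assessed at the wave 2 time point at some of the sites (this was at site discretion"). The reason given is the lag between the two mailings.
- Delayed arm, SAP I.F: status is examined at the same time point as the early arm, "meaning at the time of mailing per Data Partner, via the locked data (using the wave 1 and 2 dates").
- Delayed arm, Protocol VI: the fresh pharmacy data "that was generated and locked at the time of randomization will be used to assess trial eligibility".
- Protocol VII.B: the OAC exclusion is "determined at randomization for the early intervention cohort and 12 months post-randomization for the delayed intervention cohort". The Protocol synopsis, the schematic footnotes in Protocol VI and SAP I.F, and the exclusion list in SAP I.E also put the delayed-arm determination about 12 months later.
- SAP II bullets: the early mITT set is the members who were mailed. The delayed set is "Delayed intervention members who were not on treatment at the date of mailing".

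**The concern.** The primary endpoint is at least one OAC fill, or the INR proxy, during follow-up. A patient already on OAC when follow-up starts will usually meet it at the next refill, whatever the letter did. Randomization is protected only if such patients are removed from both arms to the same extent, and SAP II relies on exactly that.

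The described checks leave two routes by which this can fail, in opposite directions:

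- **Early arm screened less completely.** At a site with no wave 2 re-check, an early-arm patient who started OAC after the randomization check could be mailed and kept, while the delayed-arm counterpart is removed at the pseudo-wave date. This inflates the effect.
- **Delayed arm screened less completely.** If delayed-arm status comes only from data locked at randomization, starts before the mailing date go unseen. In the early arm a recent dispensing can stop the mailing (Protocol IX). This masks the effect.

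**Working it through.** **1. Can the named sources deliver the common exclusion?** It needs a view of fills and enrolment from randomization to the mailing date.

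| Arm | Source named for the screen | Covers randomization to mailing? |
|---|---|---|
| Early, wave 2, site re-checked | Re-check at wave 2 | Yes, subject to claims lag |
| Early, no re-check | Check at randomization | No |
| Delayed | Locked data, read at the wave dates (SAP I.F) | No, if locked at randomization as in Protocol VI |

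SAP I.D says the Sentinel data available at analysis will be used for the endpoints. Those data would cover the gap in both arms, but no text assigns them to this screen.

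**2. The plan's own figures.** For 33% against 38%, two-sided 5%, with continuity correction, the totals are 3926, 4836 and 6802. Divided by 0.70 for attrition they give 5609, 6909 and 9718, against the stated 5610, 6910 and 9718. The stroke/TIA powers reproduce at 40,000 × 0.70 = 28,000 per arm (46.4% and 80.4%, stated 46% and 80%). I therefore use 28,000 per arm. None of these figures is in dispute.

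**3. How fast starters accumulate.** Inputs: 33% one-year initiation (SAP I.G) and an assumed constant hazard.

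- Monthly hazard h = −ln(0.67)/12 = 0.0334.
- Started after L months: g = 1 − exp(−hL) = 3.3%, 6.5%, 9.5% and 12.5% for L = 1, 2, 3 and 4.

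**4. Shift in the arm difference.** A retained starter reaches the endpoint with probability r (refill during follow-up) instead of 0.33. With a share s of one arm unscreened, shift = s × g × (r − 0.33). The documents give none of L, s or r, so all three are assumptions.

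- L = 2, r = 0.90: 0.0646 × 0.57 = 3.7 points in the affected patients.
- L = 2, r = 0.70: 0.0646 × 0.37 = 2.4 points in the affected patients.

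| L (months) | s = 10% | s = 20% | s = 50% |
|---|---|---|---|
| 1 | 0.12–0.19 | 0.24–0.37 | 0.61–0.94 |
| 2 | 0.24–0.37 | 0.48–0.74 | 1.2–1.8 |
| 4 | 0.46–0.71 | 0.92–1.4 | 2.3–3.6 |

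(Points of arm difference; each range runs from r = 70% to r = 90%.)

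**5. Against the precision of the trial.** SE = √(2 × 0.33 × 0.67 / 28,000) = 0.40 points. At L = 2 and s = 20% the shift is 1.2 to 1.9 standard errors. With no true effect, a two-sided 5% test would then reject about 22% to 46% of the time. With the same exclusion applied in both arms from equally complete claims, s = 0 and the shift is zero.

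**The case against.** The strongest reply is that the SAP already prescribes symmetry. The both-arm exclusion is a forward-looking analysis rule, while the site-discretion sentence is in the past tense and can describe only what was checked for mailing. The governing sentence in SAP II, like Protocol XIV.B, requires early patients to have met eligibility as well as been mailed, so the shorter bullet need not be read as dropping that condition. The locked data in SAP I.F are not dated there; the randomization date comes from Protocol VI. The 12-month wording can mean when the check is run, since the criterion in both arms is a fill in the 12 months before randomization.

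All of this stands, and it rules out two stronger readings that a reader might infer. One is that the plan has settled on different screens by arm. The other is that delayed-arm eligibility is judged on fresher claims: Protocol VI says those data were locked at randomization, and the 1–4 month against 1 month lag is a difference between protocol and SAP, not between arms. Protocol IX also lists a recent dispensing as a reason not to mail, which would limit contamination of the early arm.

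The reply does not supply the missing step: the source that carries out the exclusion at sites without a re-check, and how data locked at randomization show status at a later mailing date. The as-randomized analysis with a 365-day washout is a partial check only. It is a sensitivity analysis in a different population, which includes treated and uncontactable patients.

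**Conclusion.** The concern holds as an unresolved contradiction about who enters the primary analysis. It does not show that bias has occurred or in which direction. The SAP II claim of equal time points is not supported by the operations in SAP I.F and Protocol VI.

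The size is conditional. A shift of about 0.5–0.7 points rests on an assumed 2-month gap, 20% of one arm affected and 70–90% refilling. Across the assumed ranges in the table it runs from 0.1 to 3.6 points, against a planned effect of 5 points. No text supports a particular share. On the re-check route the clearest exposure is wave 2 patients at sites that did not re-check, whose number is not given. The shift is zero if the both-arm exclusion is applied symmetrically. Because small one-sided contamination exceeds the standard error in a trial of this size, the rule should be settled before database lock.

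**What to change.** In SAP I.F and II, state one rule for the analysis set. At the analysis cut, each Data Partner applies the existing both-arm exclusion by reading OAC status and enrolment for both arms from the same mature claims extract.

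- **Index date:** the actual wave mailing date (early arm) or the pseudo-wave date (delayed arm) for that Data Partner.
- **Look-back for OAC:** from 12 months before randomization to the index date, in both arms.
- **Application:** the exclusion applies in the early arm even if the patient was mailed. Everything it uses precedes the letter, so it does not condition on the intervention.
- **Sources:** remove the locked data as the source for this screen, and state that the site-discretion re-check governed mailing only.
- **Reconcile:** the Protocol synopsis, section VI with its footnotes, and VII.B; SAP I.E, I.F with its footnotes, and II. Where the 12-month wording means only when the check is run, or eligibility for the delayed mailing, say so.
- **Report:** numbers excluded by arm, Data Partner and wave.

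The cost is SAP and protocol wording, one change to the distributed cohort program, and slightly fewer analysed patients. The claims needed should already be in the Sentinel database by the analysis cut.
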